# SAP and protocol version

SAP version and date	This SAP is version 1.0, dated 24.06.2025
Protocol version	This document has been written based on information contained in
	the study protocol version 1.0, dated 22.12.2023

# **Abbreviations**

CBT-I	Cognitive behavioural therapy for insomnia
dCBT-I	Digital Cognitive behavioural therapy for insomnia
ISI	Insomnia severity index
IQR	interquartile range
NAV	Ny arbeids- og velferdsforvaltning
NTNU	Norwegian University of Science and Technology
OR	Odds ratio
RCT	Randomised controlled trial
RR	Risk ratio
SAP	Statistical analysis plan
SD	Standard deviation
WAS	Work ability Scale
WAI	Work ability index

#### 1. Introduction

This statistical analysis plan (SAP) should be read in conjunction with the published study protocol named "Effectiveness of digital Cognitive Behavioural Therapy for Insomnia in patients with musculoskeletal complaints and insomnia in primary care physiotherapy: study protocol for a randomised controlled trial" published in BMJ Open ([name] et al., 2024). The information presented in this document provides a description of the "Statistical analysis plan" section. The data will be available for the researchers after the last participant has responded to the questionnaire at 6 months follow-up, expected to be September 31st, 2025.

#### 1.1. Purpose and scope of the statistical plan

This document provides the proposed analysis of the of the primary and secondary outcomes from the clinical trial named "Effectiveness of digital Cognitive-Behavioural Therapy for Insomnia in patients with musculoskeletal complaints and insomnia in primary care physiotherapy: a randomized controlled trial". Any deviations from the analyses outlined in this SAP will be described and justified in all papers from the project, including any additional analyses recommended by journal editors and referees. Modifications will be thoughtfully considered and aligned with the broad principles outlined here. The main purpose of this SAP is to describe the analyses. Any analyses in subsequent studies will follow the principles presented in this SAP but are not described in detail. Wherever feasible, data management and modeling decisions will be made before treatment allocation is revealed. The final analysis strategy will be available upon request when the papers are submitted.

# 1.2. Background and rationale

More than half of individuals seeking physiotherapy due to musculoskeletal complaints report insomnia symptoms (Pfeiffer, Triplett & Siengsukon, 2024). Those with both insomnia and chronic pain experience greater pain intensity (Alsaadi et la., 2014) lower pain tolerance (Woelk et al., 2020), and a lower probability of pain relief (Pakpour et al., 2018). The bidirectional association between sleep and pain (Santos et sl., 2023) indicates that sleep should be included in the treatment plan for individuals with musculoskeletal complaints and comorbid insomnia.

Cognitive Behavioural Therapy for Insomnia (CBT-I) is the recommended treatment for insomnia due to its long-term effectiveness (Riemann et al., 2017). However, lack of therapists and long waiting lists limit its availability (Grandner & Chakravorty, 2017). To address this issue, self-guided and digital versions of CBT-I (dCBT-I) have been developed (Hasan et al., 2022; Starke et al., 2024). These digital solutions have the potential to reach a broader patient population, and can easily be integrated and combined with existing treatment regimes.

#### 1.3. Objectives

#### 1.3.1. Primary objective

The primary objective of this randomised controlled trial is to evaluate the effectiveness of dCBT-I in addition to physiotherapy treatment in patients with chronic musculoskeletal complaints and insomnia, compared with physiotherapy treatment only. The primary outcome is insomnia severity at 3-month follow-up.

# 1.3.2. Secondary objectives

- I. Evaluate the effectiveness of dCBT-I on physical function, pain intensity, health-related quality of life, mental distress, work ability, and self-reported use of sleep and pain medication at 6 weeks, 3 months follow-up (primary outcome) and 6 months follow-up.
- II. Examine the difference in the proportion of participants in the intervention and the control group that achieves a clinically relevant (i.e., 8-point Insomnia Severity Index [ISI] decrease) improvement in insomnia severity at 6 weeks, 3 months follow-up (primary outcome) and 6 months follow-up.

#### 1.3.3. Additional objectives

If the data material allows it, we will in additional publications examine the following objectives:

- Assess the long-term effects of dCBT-I on primary and secondary outcomes at 12-months follow up.
- II. Compare sick leave days, use of prescribed medication (eg, psychotropics, sedatives) and healthcare resource utilization, using national registry data at 12-months post-treatment between the intervention and the control group.

#### 2. Study design

#### 2.1. Type of design

The study is a two-arm multicentre randomised controlled trial (RCT).

#### 2.2. Randomization and treatment assignment

Participants will be block randomized in a 1:1 ratio to either the intervention group (usual treatments provided by a physiotherapist + dCBT-I) or the control group (usual treatments provided by a physiotherapist). Randomization will be performed by a researcher using a secure digital platform for multicentre clinical studies, eForsk. In eForsk, a third-party user from the Section for Research at St Olav's hospital will set up the randomization procedure, blinded to the project group. [name] will conduct the allocation.

#### 2.3. Intervention

#### 2.3.1. Usual treatments provided by a physiotherapist

Participants in the control group will receive usual treatments provided by the physiotherapist. This includes any diagnostic procedure, treatment or referral the physiotherapist finds relevant based on the medical history, clinical findings and pragmatic, daily clinical practices to address musculoskeletal complaints. Participants are allowed to seek care and treatment elsewhere as they find relevant. After the completion of the long-term follow-up at 12 months, participants in the control group will be offered to use the app given to the intervention group.

# 2.3.2. dCBT-I in addition to usual treatment provided by physiotherapists

Participants randomised to dCBT-I in addition to usual treatment provided by a physiotherapist will receive the sleep intervention delivered via a smartphone app. The trial will use a Norwegian dCBT-I programme named *Assistert Selvhjelp* (In English: 'Assisted Self-Help', website: https:// assistertselvhjelp.no/). The app consists of six interactive self-managing modules based on the principles from face-to- face CBT-I including sleep hygiene, stimulus control, sleep restriction, cognitive therapy, and relaxation training. Sleep restriction is covered in module 3, while both stimulus control and sleep hygiene are included in module 4. The modules also consist of tasks such as write sleep diary, practice sleep restriction and change lifestyle behaviour, learning material like quizzes and materials explaining and educating the patients about important aspects about sleep. These activities facilitate self-management and emphasize an active role in reducing insomnia symptoms. Patients will be recommended to use the app during the first six weeks after starting the physiotherapy treatment but are allowed to use the app in their own pace and during the whole project period. They will receive weekly notifications in the app.

#### 2.4. Determination of sample size

Previous studies show that the intervention effect in ISI from baseline to after intervention was 2.8-4.7 points in the intervention group compared to the control group (Vedaa et al., 2020; Wiklund et al., 2022). We therefore estimated that a sample size of 144 (72 in each group) was necessary to detect a 3-point difference with 90% power and a 2-sided alpha level of .05. Previous RCTs of dCBT-I report sample attrition rates between 12% and 50%(Christensen et al., 2016; Vedaa et al., 2020). To allow for a 30% dropout rate a 3-months follow-up, we aim to include 188 participants (94 participants in each arm) to answer our primary aim.

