#### 2.7. Stopping guidance

If the intended sample size is not reached during the intended recruitment period (ending 31 March 2025), the inclusion of participants will stop at 140 participants (70 participants in each arm), which will ensure adequate statistical power to detect a 3-point difference with 80% power, anticipating a 30% dropout rate during the follow-up.

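### Sections 2.4 and 2.7: neither 188 nor the fallback of 140 gives its stated power at 30% dropout, because the allowance was added rather than divided out

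*SAP*

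**What the plan says.** Section 2.4 gives the unadjusted requirement: "a sample size of 144 (72 in each group) was necessary to detect a 3-point difference with 90% power", at a two-sided alpha of 0.05. It cites attrition of 12% to 50% in earlier trials of digital CBT-I and then sets the recruitment target: "To allow for a 30% dropout rate a 3-months follow-up, we aim to include 188 participants (94 participants in each arm".

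Section 2.7 covers a shortfall in recruitment by 31 March 2025. Enrolment would then end at 140 (70 per arm), and the SAP makes this claim for that size: "which will ensure adequate statistical power to detect a 3-point difference with 80% power, anticipating a 30% dropout rate during the follow-up".

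Neither section gives the SD, the inflation formula or a baseline-to-follow-up correlation. The SAP is dated 24.06.2025.

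**The concern.** A dropout allowance must leave the required number after the losses, so the requirement is divided by one minus the dropout proportion. Multiplying by one plus that proportion always gives too few, and the gap widens as dropout rises. The target of 188 matches the multiplication exactly, and the fallback of 140 looks as if it was built the same way.

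These two statements tell a reader how to weigh a non-significant result. Such a result would be read as coming from a trial with 90% power (or 80% at the fallback) even after losing 30% of participants. The design does not have that power on the plan's own inputs. The SAP was finalised after the planned recruitment end and does not give the number randomised, so either size could be the relevant one.

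**Working it through.** **Inputs.** From section 2.4: 144 participants (72 per arm), difference 3 points, two-sided alpha 0.05, power 90%, dropout 30%, target 188 (94 per arm). From section 2.7: fallback 140 (70 per arm), power 80%, dropout 30%. Section 2.2 gives 1:1 allocation. The SD is not stated; it is back-solved below and is an assumption.

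**1. Reproducing 188.**
- Multiplication: 144 × (1 + 0.30) = 187.2, rounded up to 188; per arm 72 × 1.30 = 93.6, rounded up to 94. Both match the SAP.
- Division: 144/(1 − 0.30) = 205.7, so 206; per arm 72/0.70 = 102.9, so 103.

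**2. Checking 188 against the SAP's own requirement.** 188 × 0.70 = 131.6 remaining, against 144. This step needs no SD and no model.

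**3. Checking 140.** With the difference, SD and alpha held fixed, the required number scales with (z for alpha + z for power)². Going from 90% to 80% power:

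144 × (2.802/3.242)² ≈ 108.

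But 140 × 0.70 = 98 remaining. The likely origin of 140 is 108 × 1.30 = 140.4. That is an inference, because section 2.7 gives no starting number; the shortfall of 98 against 108 does not depend on it. Division gives 108/0.70 = 154.3, or 156 with equal arms (78 per arm).

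**4. Implied SD.** Solving for 90% power at 72 per arm gives 5.52 with the t-test and 5.55 with the normal approximation. An SD of 5.5 gives 90.2% at 72 per arm and 80.2% at 54 per arm (108 in total), so it reproduces the 144 and agrees with step 3.

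**5. Power at the numbers remaining** (noncentral t, two-sided 0.05, difference 3, SD 5.5):

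| Randomised | Dropout | Remaining per arm | Power | SAP states |
|---|---|---|---|---|
| 188 | 30% | 65.8 | 87.4% | 90% |
| 140 | 30% | 49 | 76.2% | 80% |
| 188 | 12% | 82.7 | 93.7% | – |
| 140 | 12% | 61.6 | 85.2% | – |
| 188 | 50% | 47 | 74.4% | – |
| 140 | 50% | 35 | 61.4% | – |

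The 12% and 50% rows span the attrition range cited in section 2.4; the SAP states no power at those rates. Across the back-solved SDs (5.50 to 5.55) and both the z and t calculations, power at 30% dropout is about 87% to 88% for 188 and 75% to 77% for 140.

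**6. Dropout actually covered.** 1 − 144/188 = 23.4%; 1 − 108/140 = 22.9%.

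**7. SD that would rescue the claims.** Both stated powers hold at 30% dropout only if the SD is about 5.25 to 5.3, which conflicts with the 72 per arm in section 2.4.

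**The case against.** The best defence is that a t-test on those who complete 3 months is not the planned analysis. Section 5.1.2 specifies a linear mixed model with baseline means constrained equal and adjustment for age, sex and pain, and section 3.3.1 includes everyone randomised. If 5.5 is an unadjusted SD, a baseline-to-follow-up correlation r reduces it by a factor √(1 − r²):

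- r = 0.20: 88.7% (188) and 77.9% (140) at 30% dropout
- r = 0.30: 90.2% and 80.0%
- r = 0.40: 92.3% and 83.1%

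A modest correlation could therefore bring the real analysis up to the stated powers. That stands as a possibility, but it does not rescue the text. Section 2.4 claims no such gain and gives no correlation. If the 144 already includes the gain, 131.6 is too few by that same calculation.

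It can also be said that the loss is only about 3 to 4 points, that no analysis changes, and that the 95% confidence intervals promised in section 3.1 will show the achieved precision. All of this is true and limits the harm. The type II error nevertheless rises from 10% to about 13%, and from 20% to about 24%. The 50% rows contradict no statement in the SAP and should be read beside the 12% rows.

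**Conclusion.** The point holds. That 188 fails to preserve 144 follows from printed figures alone, and that 140 fails to preserve 80% power follows once 144 is accepted. At 30% dropout, power is about 87% instead of 90% and about 76% instead of 80%; each size covers about 23% dropout. The power values assume a two-sample t-test on participants with 3-month data and the implied SD of about 5.5. The effect is modest and touches no analysis, but both power statements are wrong as written.

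**What to change.** Correct the statements without enrolling more participants.

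- Section 2.4: say that 188 keeps 90% power up to about 23% dropout and gives about 87% at 30%.
- Section 2.7: say that 140 keeps 80% power up to about 23% dropout and gives about 76% at 30%.
- State the SD used. If it was not about 5.5, redo these figures with the actual value.
- Because recruitment was due to have closed, add the number actually randomised, with its power or expected confidence interval half-width.
- If credit is wanted for baseline correlation in the mixed model, state the assumed correlation and show the resulting power.

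The cost is a change of SAP wording and slightly less favourable power figures. No outcome, model or significance level changes.

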#### 2.5. Framework

The study is designed as a multicentre RCT to evaluate the effectiveness of dCBT-I in addition to usual treatments provided by a physiotherapist, compared with usual treatments alone, on insomnia severity among patients with chronic musculoskeletal complaints and insomnia in primary care physiotherapy in Norway.

#### 2.6. Statistical interim analyses

Interim analyses are not planned for the trial, because major adverse events of the treatment are not expected.

#### 2.7. Stopping guidance

If the intended sample size is not reached during the intended recruitment period (ending 31 March 2025), the inclusion of participants will stop at 140 participants (70 participants in each arm), which will ensure adequate statistical power to detect a 3-point difference with 80% power, anticipating a 30% dropout rate during the follow-up.

#### 2.8. Timing of final analysis

The primary and secondary outcomes will be assessed at 6 weeks, and at 3, 6, and 12 months follow up. Because of the funding period, data from the 6-week, 3-month, and 6-month assessments will be analysed, and published together. Data from 12-month follow up will be handled separately.

#### 2.8.1. Timing of outcome assessments

The trial has five measurement points (Table 1): Baseline measurements prior to the randomization and the start of the intervention, and follow-up at 6 weeks, and 3-, 6-, and 12 months after start of intervention. Primary outcome is ISI at 3 months follow up.

**Table 1**: Assessed variables with respective questionnaires and schedule of assessment.

Name of variable	Measurement points					
	Baseline	6-weeks	3-months (Primary endpoint)	6-months	12-months	
Demographics						
Sex, age, education, economy, work schedules, shift work, living status and number of children under and/or over six years old living at home	X					
Lifestyle and health-related parameters						
Leisure time physical activity	Х		Х			
Alcohol consumption and use of drugs	Х					
Height and body weight	X					
Self-reported and prescribed sleep and pain medications	X	Х	Х	Х	Х	
		_ ^	^	Λ	Λ	
Health literacy  Work ability assessed by the Work Ability Index (de Zwart et al., 2002; El Fassi et al., 2013)	X		X		Х	
Sleep and circadian rhythms						
Insomnia severity assessed using the Insomnia severity index (Morin et al., 2011)	Х	Х	Х	Х	х	
Sleep diary (intervention only). Collected by app	Х	Х				
Beliefs and attitudes about sleep assessed using the Pain- Related Beliefs and Attitudes about Sleep (Afolalu et al., 2016)	Х					
Stress-induced sleep reactivity assessed using Ford Insomnia Response to Stress (Drake et al., 2004)	Х					
Chronotype assessed using the reduced Horne-Ostberg- Morningness-Eveningness Questionnaire (Chelminski et al., 2000)	Х					
Duration of sleep problems	Х					
Previous treatment of insomnia	Χ					
Other sleep therapy/sleep advice during the project period	Х	Х	Х	Х	Х	
Sleep self-efficacy	Χ	Х	Х			
Sleep-talking, sleepwalking, possible restless legs/sleep apnea	Х					
Pain						
Pain duration	Х					
Pain intensity last week assessed using the Örebro Musculoskeletal Pain Screening Questionnaire short form (Linton et al., 2011)	Х	X	Х	Х	X	
Patients' expectations about the treatment	X					
Fear avoidance assessed using the Örebro Musculoskeletal Pain Screening Questionnaire short form	Х					
Pain sites assessed using the Standardised Nordic questionnaires (Kuorinka et al., 1987)	Х					
Musculoskeletal health assessed using the Musculoskeletal health questionnaire (Hill et al., 2016)	Х	Х	X	Х	Х	
Pain self-efficacy assessed using the Pain Self-Efficacy Questionnaire-2 items (Nicholas et al., 2015)	Х					
Other physical and mental health problems						
Somatic and mental conditions	Х					
Health-related quality of life assessed using the EuroQol EQ5D-5L (Solberg et al., 2015)	Х	Х	Х	Х	Х	
Mental distress assessed using the Hopkins Symptom Check List -5 item version (Strand et al., 2003; Derogatis et al., 1974)	Х	Х	Х	Х	Х	
Fatigue assessed using the fatigue Severity Scale (Lerdal et al., 2005)	Х	Х	Х			

Work productivity and activity impairment assessed using	Х	-	Х		Х
the Work Productivity and Activity Impairment questionnaire					
(Reilly et al., 1993)					
Sick leave. Register based data	Χ	Х	X	Х	X
Health service utilisation. Register based data	Χ	Х	Х	Х	Х
Physiotherapy treatment					
Patients' beliefs about the treatment	Χ				
Treatment approaches		Х	Х		
Sleep focus during treatment		Х	Х	Х	Х
Subjective experience of changes in pain and sleep		Х	Х	Х	Х
App (only for intervention group)					
Patients' beliefs about the digital sleep therapy	Χ				
Digital literacy skills (use of app)	Χ				
Adherence to treatment components		Х	Х	Х	Х
eHealth Usability Benchmarking Instrument assessed using		Х			
the eHealth UsaBility Bechmarking Instrument (Broekhui &					
van Velsen et al., 2022)					
Negative effects of the sleep therapy		Х			

## 3. Statistical principles

# 3.1. Confidence intervals and p-values

Estimates will be presented as mean differences or odds ratios with 95% confidence intervals. All p-values will be two-sided, and the significance level will be set to 0.05. No formal adjustment for multiple testing for secondary endpoints is made, but the issue of multiple testing will be kept in mind when interpreting results.

#### 3.2. Adherence

Sleep restriction and stimulus control are considered the most effective components in CBT-I (Furukawa, 2024). In the app, sleep restriction is covered in module 3, while stimulus control is included in module 4. Therefore, good adherence will be defined as completing at least the first four modules of dCBT-I. This will be defined based on the data on module unlocks.

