#### 3.3.2. Per-protocol analysis

The per protocol analysis will include adherent participants in the intervention group (defined as above in "3.2 Adherence").

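### The adherence rule has no time limit, so participants who first reach module 4 after the 3-month assessment can enter the per-protocol set

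*SAP*

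**What the plan says.** Section 3.2 (Adherence) sets the threshold: "good adherence will be defined as completing at least the first four modules of dCBT-I". The reason given is exposure. Sleep restriction (module 3) and stimulus control (module 4) are held to be the strongest parts of CBT-I. On measurement the section adds: "This will be defined based on the data on module unlocks". It names no date, week or visit.

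Section 3.3.2 (Per-protocol analysis) carries this definition over: "The per protocol analysis will include adherent participants in the intervention group". It refers back to 3.2 and adds no window, outcome or time point.

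Section 2.3.2 describes the permitted use of the app. The advice is: "Patients will be recommended to use the app during the first six weeks after starting the physiotherapy treatment". Participants are nevertheless "allowed to use the app in their own pace and during the whole project period".

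Sections 2.8.1 and 5.1.1 make ISI at 3 months the primary outcome, and 2.8.1 counts follow-up from the start of the intervention. Under the Introduction, researchers receive the data once the final 6-month questionnaire is in. Section 2.8 adds that "data from the 6-week, 3-month, and 6-month assessments will be analysed, and published together".

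**The concern.** A per-protocol analysis of the primary endpoint should describe participants who had received the active content when the endpoint was measured. An untimed rule does not secure this, for two reasons.

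First, the exposure can come after the outcome. Someone who unlocks module 4 in month 5 had not received stimulus control when the 3-month ISI was recorded, yet that ISI is analysed as a treated value. This contradicts section 3.2's own reason for choosing four modules.

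Second, membership is conditioned on what happens after the endpoint. Participants who still sleep badly at 3 months may have more reason to go on with the app, and could then qualify partly because of their 3-month result. Those who have recovered may stop early and not qualify.

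At stake are the per-protocol estimate and the reported adherence rate. If the cut-off stays open, it may also be chosen after the data have been seen.

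**Working it through.** The SAP states no figure that can be reproduced here, so the check is mainly a reading of the sections together.

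**Step 1: can a late unlock occur?** Yes. Section 2.3.2 recommends six weeks but allows use for the whole project period.

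**Step 2: can it be in the data?** Yes. Release follows the last 6-month response, so unlocks made between month 3 and month 6 can be on record for every participant when the 3-month result is analysed.

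**Step 3: does it qualify the participant?** Yes. Section 3.2 asks only whether the first four modules were reached, and 3.3.2 adds nothing.

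**Step 4: does another part of the SAP supply a window?** No. Table 1 in section 2.8.1 schedules adherence to treatment components at 6 weeks and at 3, 6 and 12 months, but no section uses those time points to classify anyone, and 3.2 relies on unlocks.

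**Step 5: what size could the dilution have?** This is an illustration, not an estimate. The inputs are:

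- D = 3 ISI points, the planning difference in section 2.4, taken here as the 3-month effect in timely users against control.
- f = the share of the per-protocol intervention group that reaches module 4 only after 3 months. The SAP gives no value, so a range is assumed.
- k = the fraction of D that late users already have at 3 months, assumed to be 0 or 0.5.

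Expected 3-month per-protocol difference = D × [1 − f × (1 − k)].

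| f (assumed) | k = 0: 3 × (1 − f) | k = 0.5: 3 × (1 − 0.5f) |
|---|---|---|
| 5% | 2.85 | 2.93 |
| 10% | 2.70 | 2.85 |
| 20% | 2.40 | 2.70 |
| 30% | 2.10 | 2.55 |

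The k = 0 column is the extreme case, since a late user may have worked through modules 1-3 by month 3. The formula also assumes that late and timely users have the same prognosis. If they differ, the estimate can move in either direction, and the table does not capture that.

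**The case against.** The strongest reply is that section 3.3.2 names no visit, so the SAP never says that a late unlocker will be treated as exposed at 3 months. That is correct as far as it goes: a 3-month per-protocol result is inferred from 3 months being the primary endpoint. But the SAP gives one definition of the set and no other, and under that definition the late unlocker belongs to it.

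A second reply is that few people will be affected. Use is recommended for six weeks with weekly notifications, and 3 months is about 13 weeks, more than twice that period. This stands as a limit on the size. It does not repair the rule, and if few are late the correction costs little.

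A third reply is that Table 1 already plans adherence by visit. It does, but nothing links that row to the definition in 3.2. The protocol, not seen here, might give a window, but section 3.3.2 refers only to section 3.2.

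A reader might also infer three stronger points that the SAP does not support:

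- **That the per-protocol estimate must be biased toward no effect.** Dilution acts in that direction, but selection may act either way.
- **That adherence largely reflects enrolment date.** Every participant still in follow-up has about six months before release, so enrolment date matters only for those who first reach module 4 after about month 6. The SAP also gives no extraction date for the unlock log.
- **That a 6-week per-protocol result is distorted in the same way.** Section 5.1.2 sets up the ISI model for 3 and 6 months only, and no 6-week per-protocol analysis is specified.

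**Conclusion.** The point holds for the per-protocol analysis. As written, sections 3.2 and 3.3.2 define the set by unlocks at any time, including after the primary endpoint, which conflicts with the exposure reason given for the four-module threshold. This is more than a missing detail, because the stated rule followed literally gives the wrong set.

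The size cannot be determined from the SAP. Under the assumptions shown, dilution alone would take a 3-point difference to between 2.93 (5% late, half the effect) and 2.10 (30% late, no effect). The true share may be small, and the net direction is not known once selection is considered. The dates in the unlock log would show the share.

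The primary intention-to-treat analysis in sections 3.3.1 and 5.1.2 is untouched. The change should be made, but the trial's main result does not depend on it.

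**What to change.** Add to section 3.2 that, for the per-protocol analysis of the primary endpoint, *modules 1-4 must be unlocked on or before the participant's own 3-month assessment, with follow-up time counted from the start of the intervention as in section 2.8.1*. Participants who unlock module 4 later are non-adherent for that analysis. For a participant without a 3-month response, the scheduled date can stand in for the assessment date.

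Use this single set throughout the per-protocol mixed model. Separate sets for each visit would not fit one joint repeated-measures model with a common baseline mean, and the populations would differ between visits.

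The work is one sentence in the SAP and a date filter on the unlock log, best settled before the data are released. The costs are a somewhat smaller per-protocol set, a lower reported adherence rate and somewhat stronger selection of faster completers. Participants who reach module 4 between 3 and 6 months will also be left out of the 6-month per-protocol estimate, which the report should state along with their number.
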